5 STUDY POPULATION CHARACTERISTICS

5.1 Study participant disposition

Summaries of reasons for screen failures (for ES), disposition of participants (for ES), disposition of analysis sets (for RS), disposition and discontinuation reasons in the Initial Treatment Period (for RS) and the Maintenance Treatment Period (for MS), as well as the participants who discontinued due to AEs in the Initial Treatment Period (for RS) and Maintenance Treatment Period (for MS) will be produced. The disposition of participants for all participants screened will include the number of participants included in each analysis set (ES, RS, SS, FAS, AMS, MS, PPS, and PK-PPS) overall and by site.

Participants are defined as completing the Initial Treatment Period if they have a Week 16 visit, or if they fail to attend the Week 16 visit but attend at least one visit in the Maintenance Treatment Period.

The following listings for participant disposition will be provided: participants who did not meet study eligibility criteria (for ES), participant disposition (for ES), participant discontinuation (RS), visit dates (for RS), participant analysis sets (for ES), participants excluded from efficacy analysis (for RS).

To assess participant disposition (entry and periods in the study) during the COVID-19 pandemic, study participant disposition will also be assessed by period of the COVID-19 pandemic (pre – during – post), by comparing the dates of visits (or events) to the dates of the COVID-19 pandemic period. The dates to categorize the periods of the COVID-19 pandemic (pre/during/post) are defined below:

- Pre-COVID-19 pandemic period: Period prior to COVID-19 pandemic start date defined as 11-Mar-2020
- COVID-19 pandemic period: Period from 11-Mar-2020 through the COVID-19 pandemic end date which is currently not defined at the time of approval of the SAP
- Post-COVID-19 pandemic period: Period after the declaration of the end of the pandemic

5.2 Impact of COVID-19

A listing of visits affected by COVID-19 will be presented based on the ES including the visit, date of visit, relationship to COVID-19, impact category and a narrative (short description) of the event. These data will be summarized for non-randomized participants and by treatment group and overall, for enrolled participants.

A summary of study visits by COVID-19 pandemic period (pre – during – post) will be presented for participants enrolled prior to and during the pandemic.

In addition, in order to assess the potential impact of COVID-19 on the collection and reporting of efficacy data, a separate summary on the RS will be presented to display missing data as well as data collected via an alternative modality (e.g.: phone, video call) for efficacy endpoints included in the hierarchy (Section 4.5). For these displays, missing data will be presented only for visits affected by COVID-19, as reported on the dedicated eCRF page. Missing data at other visits and for other reasons will not be included. Note that the remote contingencies for COVID-19 or other exceptional circumstances are not applicable to efficacy assessments and documentation (eg, lesion-based assessments, photography) that require direct face-to-face physician/participant interaction.

5.3 Protocol deviations

Summaries, based on the RS and the MS, displaying the number and percentage of participants with an important protocol deviation (including a summary of participants excluded from the PPS or PK-PPS due to important protocol deviations) by treatment group in the Initial Treatment Period and in the Maintenance Treatment Period, respectively, will be provided. A separate summary of participants with protocol deviations related to COVID-19 will be provided.

A by-participant listing of protocol deviations will be provided. Protocol deviations (eg, missing assessments or visits) related to COVID-19 will be listed separately.

6 DEMOGRAPHICS AND OTHER BASELINE CHARACTERISTICS

All summaries detailed in this section will be performed on the RS by treatment group. Summaries for demographics and other baseline characteristics will also be repeated on SS and MS. If the RS and SS are identical, the SS summaries will not be created.

6.1 Demographics

Demographic variables will be summarized by treatment group and overall.

The following continuous variables will be summarized using descriptive statistics (number of study participants, mean, SD, minimum, median, and maximum).

- Age (years)
- Height (cm)
- Weight (kg)
- BMI (kg/m²)

BMI (kg/m²) will be calculated as:

$$\text{BMI} = \frac{\text{Weight (kg)}}{(\text{Height (m)})^2}$$

The following categorical variables will be summarized generally using frequency counts and percentages.

- Age group (≤ 18 , $19 < 65$, ≥ 65 years)
- Age group ($18 < 65$, $65 < 85$, ≥ 85 years)

- Age group (<40, 40-<65, ≥65 years)
- Body weight (≤100 kg, >100 kg)
- Gender
- Race
- Ethnicity
- Ethnic subgroup
- BMI (<25 kg/m², 25 to <30 kg/m², ≥30 kg/m²)
- Region
- Smoking history
- Country

By-participant listing of demographics for all study participants screened will be provided.

Childbearing potential and lifestyle will be collected at Screening.

6.2 Other Baseline characteristics

The following Baseline disease characteristics will be summarized by treatment group:

- Lesion counts by anatomical region and lesion type, total lesion counts across anatomical regions by lesion type, Hurley Stage by anatomical region and worst overall Hurley Stage across anatomical regions
- IHS4 score, individual items of the HSSDD, HS-Physician's Global Assessment, DLQI total score and HiSQOL domain and total scores
- hs-CRP
- Duration of disease (years)

Duration of disease (years) will be calculated as:

$$\text{Disease Duration} = \frac{(\text{Date of randomization} - \text{Date of HS Diagnosis}^1)}{365.25}$$

¹If the date of HS diagnosis is partial, it will be imputed to the most recent feasible date (ie, last day of the month if only day is missing, or the last day of the year if day and month are missing). Note that if the date of randomization is missing then the duration of disease will be derived using the date of screening. If the imputed date results in a participant having a disease duration of less than 6 months and the inclusion criterion related to having HS for at least 6 months is confirmed to not have been violated, then the participant's duration of disease will be set to 6 months. If that criterion has been violated, then the participant's duration of disease will be the imputed value of less than 6 months.

- Duration of disease (<median, ≥median)

The median disease duration will be calculated based on all participants in the analysis set used for the summary.

- Baseline antibiotic use (yes, no) (According to the randomization strata)
- Baseline antibiotic use (yes, no) (Derived)
- Hurley Stage at Baseline (According to the randomization strata)
- Hurley Stage at Baseline (Derived)

In addition, the following Baseline disease characteristics will be summarized by the derived Baseline Hurley Stage and by the derived Baseline antibiotic use and treatment group for the RS:

- IHS4 score
- “worst skin pain score” and “average skin pain score” in the HSSDD
- HS-Physician’s Global Assessment
- DLQI total score
- hs-CRP
- Duration of disease (years)
- Total lesion counts

6.3 Medical history and concomitant diseases

Previous and ongoing medical history will be summarized by treatment groups, system organ class (SOC), and preferred term (PT) using MedDRA[®]. Medical procedures are not coded.

The following listings for medical history and concomitant diseases will be provided: medical history, HS history, concomitant medical procedures, previous and ongoing medical history glossary, previous and ongoing medical history conditions, and procedure history.

6.4 Prior and concomitant medications

Prior medications include any medications that started before the start date of study medication. Concomitant medications are any medication that has a start date on or after the start date of study medication, or any medication that has a start date on or before the last dose of study medication + 28 days (whether placebo or bimekizumab).

Any medication that started before the first dose of IMP and continued after will be classified as both prior and concomitant. Such medications will therefore be counted in the tabulations for both prior and concomitant medication.

Details of imputation methods for missing or partial dates are described in Section 4.2.4.

The number and percentage of participants taking prior medications will be summarized by treatment group, overall and by ATC class, presenting Anatomical Main Group (ATC Level 1), Pharmacological Subgroup (ATC level 3), and PT. Prior antibiotic medications will be summarized similarly.

The number and percentage of participants taking concomitant medications will be summarized similarly for the Initial Treatment Period and Maintenance Treatment separately. The number and percentage of participants taking concomitant antibiotic medications, antihistamines, and analgesics will be summarized separately by treatment group, overall, and by ATC class,

presenting Anatomical Main Group (ATC Level 1), Pharmacological Subgroup (ATC level 3), and PT for the Initial Treatment Period and Maintenance Treatment Period separately.

Separate summaries will be presented for participants taking rescue medication for the Initial Treatment Period and Maintenance Treatment Period separately, identified by a 'yes' response to the 'Is this a rescue medication' question on the electronic case report form (eCRF). This summary will be performed separately for analgesic use and antibiotic use.

Additional summaries for the Initial Treatment Period and Maintenance Treatment Period will be presented for participants taking systemic antibiotic medications that qualify as intercurrent events as described in Section 3.9.

The number and percentage of study participants with concomitant vaccines for COVID-19 will be summarized by treatment group, overall and by World Health Organization Drug Dictionary Standardized Drug Grouping (SDG), presenting SDG subgroup, and preferred term. The SDG subgroup Vaccines for COVID-19 will be used to identify vaccines for COVID-19 using the narrow scope; this subgroup is divided further into separate subgroups which is the level that will be presented. The number of individual occurrences of the vaccine for COVID-19 will also be summarized.

A listing of concomitant vaccines for COVID-19 will be provided.

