2.3.2.3 Safety Follow-up Visit

All study participants not continuing in the extension study, including those withdrawn from IMP as well as those completing all study visits, will have an SFU Visit 20 weeks after their final dose of IMP.

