6.4.1 Assignment of medications to study period

The following rules will be used to assign a concomitant medication to a study period:

- **Initial Treatment Period:** a medication will be assigned to the Initial Treatment Period if it has been taken at least once between the first administration of IMP on Day 1 up to Week 16. This includes medications that started prior to the Initial Treatment Period and those that continued into the Maintenance Treatment Period.
- **Maintenance Treatment Period:** a medication will be assigned to the Maintenance Treatment Period if it has been taken at least once between Week 16 and the final visit. This includes medications that started prior to the Maintenance Treatment Period.

Thus, a medication taken from the time of the first drug administration in the Initial Treatment Period to any timepoint after Week 16 will be assigned to both the Initial Treatment Period and the Maintenance Treatment Period.

Methods for dealing with partial dates are specified in Section 4.2.4.

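### SAP Section 6.4 joins its two start-date conditions for concomitant medication with *or*, so the 28-day limit after last dose excludes nothing and the rule conflicts with the sentence that follows it

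*SAP*

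**What the plan says.** Section 6.4 gives three statements in sequence.

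- Prior: "Prior medications include any medications that started before the start date of study medication".
- Concomitant, by either of two conditions. The first reads "Concomitant medications are any medication that has a start date on or after the start date of study medication"; the alternative, which carries the 28-day limit, reads "or any medication that has a start date on or before the last dose of study medication + 28 days". Both conditions concern the start date; neither concerns the stop date.
- Both: "Any medication that started before the first dose of IMP and continued after will be classified as both prior and concomitant".

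Section 6.4.1 then assigns concomitant medications to study periods by intake. In the first window, Initial Treatment, a medication counts "if it has been taken at least once between the first administration of IMP on Day 1 up to Week 16"; in the second, Maintenance, it counts "if it has been taken at least once between Week 16 and the final visit". Neither window refers to the last dose or to 28 days.

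The general, antibiotic, antihistamine and analgesic tables of concomitant use are presented by period. The vaccine table is not: "The number and percentage of study participants with concomitant vaccines for COVID-19 will be summarized by treatment group", with no split by period there or in the accompanying listing.

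Section 2.3.2.3 says that participants not continuing in the extension study "will have an SFU Visit 20 weeks after their final dose of IMP".

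**The concern.** A definition with a stated cut-off should exclude something. This one sets a lower bound in one condition and an upper bound in the other, then accepts a medication that meets either. The two bounds cancel.

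Two kinds of record are at stake. At the early end, a drug stopped before first dose is concomitant under one sentence and prior only under the next. At the late end, a drug started well after the last dose is concomitant although the plan sets a 28-day limit. No neighbouring sentence corrects that.

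A programmer must either apply a rule that selects everything or substitute one that is not written down, and two programmers could substitute different ones. The tables and listings meant to show what was taken alongside study drug would then depend on that choice.

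**Working it through.** **Notation.** *s* = start date, *F* = first dose, *L* = last dose, with *F* ≤ *L* (Section 6.4). The Safety Follow-up visit falls 20 weeks after last dose, at *L* + 140 days (Section 2.3.2.3). The plan gives no figure to reproduce here.

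**Logic of the rule.** Concomitant if *s* ≥ *F* or *s* ≤ *L* + 28. To be excluded, a date must satisfy *s* < *F* and *s* > *L* + 28 together, which needs *L* + 28 < *F*. That is impossible when *F* ≤ *L*.

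**Enumeration.** All start days from *F* − 3650 to *L* + 140 were tested:

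| Last dose | Start days tested | Excluded by the rule |
|---|---|---|
| Week 0 | 3791 | 0 |
| Week 8 | 3847 | 0 |
| Week 14 | 3889 | 0 |
| Week 46 | 4113 | 0 |

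**Test records** (first dose day 0; last dose Week 46 = day 322; limit = day 350). *Overlap* means start ≤ *L* + 28 and stop ≥ *F*.

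| Record (start, stop) | As written | *Or* changed to *and* | Overlap |
|---|---|---|---|
| Stopped before dosing (−400, −200) | yes | no | no |
| Ongoing from before dosing (−400, 100) | yes | no | yes |
| During treatment (50, 60) | yes | yes | yes |
| Starts *L* + 28 (350, 360) | yes | yes | yes |
| Starts *L* + 29 (351, 360) | yes | no | no |
| Starts *L* + 100 (422, 430) | yes | no | no |

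Row 1 as written contradicts the sentence on medications that continue past first dose. Changing *or* to *and* breaks the same sentence in row 2. Only the overlap rule respects both that sentence and the 28-day limit.

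**What Section 6.4.1 filters.** It requires intake on or after Day 1, so row 1 drops out of the by-period tables. It does not remove late starts:

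- *Early stoppers who remain in the study.* The treatment policy strategy in Section 4.2.1.4 expects some participants to do this. Illustration: last dose at Week 4 puts the limit at Week 8. An antibiotic first taken at Week 12 starts 56 days after last dose, 28 days past the limit, yet it falls inside the Initial Treatment Period window.
- *Follow-up.* If the final visit is the Safety Follow-up visit, the window runs 140 − 28 = 112 days past the limit. If it is Week 48, a completer last dosed at Week 46 (Section 7) has a window ending about 14 days after last dose, inside the limit, and the excess is zero.

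**Vaccine outputs.** A vaccination given on one day before first dose meets the second start-date condition, so it is concomitant. It did not continue past first dose, so under the next sentence it is prior only. With no period split, Section 6.4.1 does not settle the matter.

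**The case against.** The best defence is that the plan should be read as a whole. The sentence on medications that continue past first dose shows what was meant for drugs started earlier, and Section 6.4.1 applies an intake test to the main tables. That stands. A reader might infer that every medication ever recorded will be reported as concomitant, or that the vaccine table is certain to count pre-dose vaccinations. The documents do not support either. At the early end there is a contradiction between adjacent sentences, and the by-period tables are protected.

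A reader might also infer that every participant's Maintenance window is stretched by 112 days. That requires the final visit in Section 6.4.1 to be the Safety Follow-up visit, which the section does not say. Section 10.1.2.1 excludes that visit explicitly and Section 10.1 includes it explicitly; Section 6.4.1 does neither. Participants who enter the extension have no such visit (Section 2.3.3). So 112 days is an upper bound for a subgroup of unstated size.

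It can also be said that a longer medication window would match adverse events, which are treatment-emergent through last dose + 140 days (Section 10.2.1). That is a possible design, but Section 6.4 states 28 days. If a longer window is wanted, the number should change.

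Lastly, no test is touched. Intercurrent events (Section 3.9) and analgesic status (Section 6.4.2) have their own date rules, and rescue summaries use a case report form flag. This is right, and it limits the importance of the point. None of it makes the 28-day limit operate.

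**Conclusion.** The point holds as a defect in a stated rule. As written, the definition excludes no start date, so the 28-day limit has no effect, and the definition contradicts the next sentence on drugs stopped before first dose. Section 4.2.4 also presupposes a rule that discriminates: it treats a medication as concomitant by default when its dates are too incomplete to decide, which would be pointless if all medications qualified.

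The effect is confined to descriptive medication and vaccine outputs. Late-started drugs enter the by-period tables for participants who stop early and stay in the study. If the final visit includes Safety Follow-up, they also enter for up to 112 days in participants with that visit. Pre-dose vaccinations are left unresolved. The number of affected records cannot be derived from the SAP. A reader might suppose that the concomitant antibiotic and analgesic tables feed the efficacy analyses; they do not.

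**What to change.** Replace the definition in Section 6.4 with: start date on or before last dose + 28 days, **and** stop date on or after first dose, or ongoing or unknown. State that the COVID-19 vaccine summary and listing use the same definition.

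No separate cap is needed in Section 6.4.1. It assigns only medications already classed as concomitant, so the limit carries through to both periods. That section should, however, say whether the final visit includes the Safety Follow-up visit.

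The cost is about one sentence of definition, a short clarification and one programming flag. No data collection and no efficacy analysis changes.

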6.4.1 Assignment of medications to study period

The following rules will be used to assign a concomitant medication to a study period:

- **Initial Treatment Period:** a medication will be assigned to the Initial Treatment Period if it has been taken at least once between the first administration of IMP on Day 1 up to Week 16. This includes medications that started prior to the Initial Treatment Period and those that continued into the Maintenance Treatment Period.
- **Maintenance Treatment Period:** a medication will be assigned to the Maintenance Treatment Period if it has been taken at least once between Week 16 and the final visit. This includes medications that started prior to the Maintenance Treatment Period.

Thus, a medication taken from the time of the first drug administration in the Initial Treatment Period to any timepoint after Week 16 will be assigned to both the Initial Treatment Period and the Maintenance Treatment Period.

Methods for dealing with partial dates are specified in Section 4.2.4.

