7 MEASUREMENTS OF TREATMENT COMPLIANCE

Due to the method of administration of the treatments, compliance will be examined in terms of completed injections.

Treatment compliance will be calculated as:

$$\frac{N_{actual}}{N_{expected}} \times 100\%$$

where N_{actual} is the total number of actual (completed) injections, and $N_{expected}$ is the total number of expected injections. In this study, dosing occurs [REDACTED] from Week 0 to Week 46, where 2 injections are administered at each given visit either with active dosing or placebo injection. It is expected that a participant should complete a total of 48 injections by the end of study. If a participant discontinues early, then the number of expected injections is based on the time of early discontinuation relative to the dosing visits. For example, if a participant discontinues after Week 8 visit and prior to Week 10 visit, the total number of expected injections will be 10.

A summary of percent treatment compliance categorized as <75% and ≥75% will be provided by treatment group for each study period (Initial Treatment Period for the RS, Maintenance Treatment Period for the MS, and the combined Initial and Maintenance Treatment Period for the AMS).

A by-participant listing of treatment compliance will be provided.

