8.4.9 Initiation of systemic antibiotic rescue therapy

See Section 3.9 for the definition of a systemic antibiotic rescue therapy.

The number of participants that use rescue antibiotic therapy will be summarized by treatment group for each period.

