8.4.23 Lesion intervention

Investigators will have the option to perform interventions in the event an acutely painful lesion occurs that requires immediate intervention.

The following rules will be used to assign a lesion intervention to a study period:

- **Initial Treatment Period:** a lesion intervention will be assigned to the Initial Treatment Period if it has been performed between the first administration of IMP on Day 1 up to and including Week 16.
- **Maintenance Treatment Period:** a lesion intervention will be assigned to the Maintenance Treatment Period if it has been performed between Week 16 through the Week 48 visit.

Methods for dealing with partial dates are specified in Section 4.2.4.

A listing of participants who receive any lesion intervention will be provided.

The number and percentage of participants who receive at least 1 lesion intervention will be summarized by treatment group for the Initial Treatment Period, Maintenance Treatment Period, and the combined Initial and Maintenance Treatment Period.

The number and percentage of participants with 2, 3, and 4 or more lesion interventions will also be summarized by treatment group for the Initial Treatment Period, Maintenance Treatment Period, and the combined Initial and Maintenance Treatment Period.

The number and percentage of participants with 2 or more lesion interventions performed on the same lesion will be summarized by treatment group for the Initial Treatment Period, Maintenance Treatment Period, and the combined Initial and Maintenance Treatment Period.

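### Maintenance-period medication tables are set on the Randomized Set, and their time window requires no Maintenance entry and has no working end

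*SAP*

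**What the plan says.** **Analysis set.** The opening of SAP Section 6 states: "All summaries detailed in this section will be performed on the RS by treatment group". It then adds: "Summaries for demographics and other baseline characteristics will also be repeated on SS and MS". Medications, which are Section 6.4, are not named in that second sentence. Section 3.1 makes the whole analysis set the default denominator for percentages.

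**Tables concerned.** Section 6.4 plans separate Initial and Maintenance summaries of concomitant medications, of antibiotics, antihistamines and analgesics, of rescue medication, and of systemic antibiotics that qualify as intercurrent events.

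**Time window.** Under 6.4.1 a concomitant medication is "assigned to the Maintenance Treatment Period if it has been taken at least once between Week 16 and the final visit". Drugs begun before Maintenance are included. Nothing requires the participant to have been dosed in Maintenance, and the final visit is not defined there.

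**Concomitant definition.** Section 6.4 reads: "Concomitant medications are any medication that has a start date on or after the start date of study medication". It continues, after the word *or*, with any medication started no later than 28 days after the last dose.

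**Follow-up.** Under 2.3.2.3, participants who do not continue into the extension, including those withdrawn from study drug, "will have an SFU Visit 20 weeks after their final dose of IMP".

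**The concern.** By-arm use of rescue antibiotics and analgesics in Maintenance will be read as a sign of disease control on bimekizumab. For that reading, both parts of the percentage should refer to people dosed in Maintenance during the time they were in it. The text fails on both.

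- **Denominator.** Participants who left in the Initial Period stay in it, so the percentage is diluted by an amount that depends on each arm's dropout.
- **Numerator.** Drugs taken by those same leavers after Week 16, and by completers after Week 48, can be counted as Maintenance use.

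The medication tables are also out of line with the rest of the SAP. Section 7 reports compliance as "Initial Treatment Period for the RS, Maintenance Treatment Period for the MS". Sections 5.1 and 5.3 use the MS for Maintenance disposition and deviations, and 10.2.2 does so for Maintenance adverse events. Section 8.4.23, whose period rule is built in much the same way, assigns a lesion intervention to Maintenance "if it has been performed between Week 16 through the Week 48 visit". Section 10.1.2.1 says explicitly that follow-up is excluded where that is meant. No reason is given for treating medications differently.

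**Working it through.** **1. When leavers reach follow-up.** Section 7 gives dosing visits from Week 0 to Week 46, 2 injections per visit and 48 injections in total, so 48/2 = 24 visits. Its example of 10 injections through Week 8 is 10/2 = 5 visits. Both fit a visit every 2 weeks, so Initial-period doses fall at Weeks 0 to 14. Section 10.2.1 equates 140 days with the 20-week follow-up, and 140/7 = 20 agrees.

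Follow-up week = week of last dose + 20:

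- Last dose Week 0: Week 20, which is 4 weeks past Week 16.
- Last dose Week 8: Week 28, which is 12 weeks past.
- Last dose Week 14: Week 34, which is 18 weeks past.
- Completer with last dose at Week 46 who does not enter the extension: Week 66, which is 18 weeks past Week 48. Those who enter the extension have no such visit.

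If the final visit includes follow-up, every leaver who attends it has 4 to 18 off-drug weeks inside the window.

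**2. What the 28-day clause does.** As written, a drug qualifies if it starts on or after first dose, *or* starts no later than last dose + 28 days. The first clause already admits every later start, so the second excludes nothing.

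Read as a cap on start dates, the limit is last dose + 4 weeks:

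- Last dose Week 8: Week 12, so new starts after Week 16 drop out.
- Last dose Week 14: Week 18, so a short interval remains.
- Last dose Week 46: Week 50.

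A cap on start dates does not remove a drug started earlier and still being taken after Week 16. The closing sentence of 6.4.1 assigns such a drug to both periods, whether or not the participant entered Maintenance.

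**3. Effect on the percentage.** Let *d* be the share of an arm not entering Maintenance, *p* the proportion of entrants with Maintenance use, and *q* the proportion of non-entrants with use counted.

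- MS percentage = *p*
- RS percentage = (1 − *d*)*p* + *dq*
- Difference, RS − MS = *d*(*q* − *p*)

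The sign depends on whether *q* is below or above *p*.

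**4. Illustration.** The SAP states no dropout rate, so *d* and the use rates are assumed. For a planned arm of 140 with about 30% use among entrants:

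| Not entering | MS | RS, no leaver counted | RS, every leaver counted |
|---|---|---|---|
| 7 (5%) | 40/133 = 30.1% | 40/140 = 28.6% | 47/140 = 33.6% |
| 14 (10%) | 38/126 = 30.2% | 38/140 = 27.1% | 52/140 = 37.1% |
| 21 (15%) | 36/119 = 30.3% | 36/140 = 25.7% | 57/140 = 40.7% |

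Two arms with the same use among entrants but 5% and 15% non-entry would show 28.6% against 25.7% on the RS from dilution alone, a gap of 2.9 points.

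For the planned placebo arm of 70 with 7 leavers and 10 users among 63 entrants, the MS gives 10/63 = 15.9%. The RS gives 10/70 = 14.3% if no leaver is counted (−1.6 points) and 13/70 = 18.6% if 3 of the 7 are (+2.7 points).

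**The case against.** **The 28 days are meant as a cap.** This is persuasive on intent. Taken literally, the two clauses together cover every medication ever recorded, including drugs stopped before Day 1, while the next paragraph of 6.4 counts a pre-dose drug as concomitant only if it continued. A cap would remove most new starts in follow-up. The text still does not say it, and ongoing drugs in non-entrants remain counted.

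**The final visit may mean the last Maintenance visit.** It may. A reader might infer that 6.4.1 explicitly includes follow-up; it does not, because the term is undefined there. But participants who stop treatment and keep attending visits, whom 4.2.1.4 foresees, can have post-Week 16 use counted on either reading, and the denominator is unaffected.

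**The sentence on repeating summaries on the MS might cover all of Section 6.** It echoes the section title, so this is arguable. Medications are not named, and the RS version would still be produced.

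**The RS is a legitimate, disclosed denominator.** It is, for a question about everyone randomized, and Section 8 uses it by default. It does not match how the SAP reports its other Maintenance tables listed above.

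**Section 8.4.9 has the same fault.** A reader might infer this, but it does not follow for the denominator. That section says "The number of participants that use rescue antibiotic therapy will be summarized by treatment group for each period", which is a count, under Section 8's RS default.

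**The tables are descriptive.** Correct. Intercurrent events are dated by 3.9, and analgesic and antihistamine user status has its own rule in 6.4.2.

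**Conclusion.** The denominator point holds on the text: the Maintenance medication tables in 6.4 are placed on the RS and so include people never dosed in Maintenance. The window point holds as a drafting fault. 6.4.1 requires no Maintenance entry and leaves its end undefined, and the *or* in 6.4 disables the only time limit. How much follow-up use would actually be counted depends on how a programmer reads those two passages.

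The size cannot be taken from the SAP. Under the assumed 5 to 15% non-entry, dilution lowers a 30% rate by about 1.5 to 4.5 points (*d* × *p*: 0.05 × 30 and 0.15 × 30). Counted use by leavers acts in the other direction, so the net error may have either sign and may differ between arms.

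Two stronger readings are not supported. The first is that the tables mix in participants who were never treated with bimekizumab: that describes only those who leave the placebo arm, since leavers from the other three arms were randomized to it. The second is that efficacy conclusions are at risk: the primary analysis, the testing sequence and the intercurrent-event dates do not use 6.4.1.

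**What to change.** Three wording changes:

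1. **Section 6.** State that the Maintenance-period medication summaries in 6.4 (concomitant, antibiotic, antihistamine, analgesic, rescue, intercurrent-event antibiotic) are on the MS.
2. **Section 6.4.1.** Run the Maintenance window from the first Maintenance dose to the Week 48 visit or the premature end of treatment visit. This matches the Week 48 end already used in 8.4.23.
3. **Section 6.4.** Reword the concomitant definition so that last dose + 28 days is an upper limit on start dates applying to every medication, and so that drugs stopped before first dose are excluded.

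No change to 8.4.9 is needed for the denominator. The cost is SAP text, a changed population flag and a revised date window in programming. No new data are needed.
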